Antidepressant Response in Older Adults
with Comorbid PTSD and MDD

Protocol ID 8111
NCT04697693

Statistical Analysis Plan

Document Version Date: January 29th, 2021

Statistical Analysis

Descriptive statistics for the sample at baseline will be computed and reported in terms of means with standard deviations. The hypotheses under investigation are that (1) individuals with comorbid PTSD and MDD will experience significant depressive symptom improvement with antidepressant treatment and that (2) cognitive and physical functioning will likewise significantly improve following antidepressant treatment. To investigate these hypotheses, paired samples t-tests will be used to analyze the within-subject change from pre- to post-treatment on depressive symptom severity (Hamilton Rating Scale for Depression [HRSD]), cognitive functioning (NIH Toolbox total score), and physical functioning (gait speed).

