Indicate which of the following populations will be included in this research

- ✓ Adults over 50

Research Support/Funding

Will an existing internal account be used to support the project?

Yes

Describe internal account

[name] University Irving Scholar account

Is the project externally funded or is external funding planned?

No

Study Location

Indicate if the research is/will be conducted at any of the following

✓ NYSPI

This protocol describes research conducted by the PI at other facilities/locations

No

Lay Summary of Proposed Research

Lay Summary of Proposed Research

In our ongoing studies of Posttraumatic Stress Disorder (PTSD) in older adults, we have found that older adults with PTSD frequently meet criteria for comorbid Major Depressive Disorder (MDD). Moreover, relative to trauma-exposed healthy controls (TEHCs), elders with PTSD manifest executive function deficits, fatigability, and mobility and physical function deficits that are consistent with what we have observed in depressed older adults. Yet, we have found that very few older adults with combined PTSD/MDD have received appropriate antidepressant treatment for their condition.

These findings give rise to the questions of (1) how effective is antidepressant treatment for depressive symptoms in the context of PTSD/MDD and (2) are cognitive and physical function deficits in PTSD/MDD patients reversible with effective antidepressant treatment?

Participants who recently completed IRB 7489 and who sign consent to participate in this open treatment study will be treated for 8-weeks with antidepressant medication. Participants will be seen in person for the week 0 (baseline) visit, where they will complete baseline testing. Participants will meet with research assistants and clinicians every two weeks virtually, via a HIPAA compliant video platform, Webex. They will then come in person for the final study visit, week 8. Week 8 will be conducted in person and will consist of repeat baseline testing. This will be the second study visit conducted in person, unless a significant clinical worsening occurs and/or the participant wishes to be seen in person for a visit. Following the 8 weeks, participants will be eligible for 3 months post protocol open treatment and will continue to receive referrals for PTSD treatment.

Background, Significance and Rationale

Background, Significance and Rationale

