In our ongoing IRB #7489, we hypothesize that chronic PTSD, over and above other contributing factors, accelerates biological aging in the brain and body, leading to adverse behavioral consequences such as frailty and cognitive decline. To test these hypotheses, 150 individuals are being recruited who are aged ≥ 50 and diagnosed with PTSD. A control group of 150 age-, sex-, and trauma exposure-matched subjects without PTSD are being recruited and assessed. Included subjects undergo comprehensive neuropsychological assessment and cerebral blood volume functional magnetic resonance imaging (CBV-fMRI) to assess regional hippocampal metabolic activity and function. Structural MRI is performed to quantify WMH, regional brain volume, and cortical thickness, while resting state fMRI measures functional connectivity within hippocampal networks. PTSD subjects and controls are compared on measures of aging within the following domains: neural (DG CBV, WMH, morphology), cognitive (processing speed, memory, executive function, pattern separation), somatic (peripheral inflammatory markers, leukocyte telomere length, and measures of oxidative stress), and behavioral (grip strength, gait speed, fatigue levels). By elucidating the interaction of chronic PTSD with aging processes, data from this project may contribute to the development of rationally designed, personalized, and age-appropriate novel treatments.

Interim analyses of PTSD subjects in this study demonstrate a high degree of comorbidity with MDD. Among participants with PTSD enrolled to date, 67.1% meet criteria for MDD and mean Hamilton Rating Scale for Depression (HRSD) is 18.1. The most prominent cognitive differences observed to date in our study between PTSD and TEHC subjects is executive dysfunction, which is common in late life depression. PTSD subjects have dramatically increased fatigability and prevalence of frailty criteria compared to TEHCs, abnormalities which are also frequently seen in our older MDD samples. Yet, we have found that less than 25% of these individuals are currently receiving an adequate dose and duration of first-line pharmacotherapy for MDD, while only one third report any past medication treatment. These data raise the question of whether patients with combined PTSD/MDD could benefit from adequate antidepressant medication treatment and to what degree their cognitive and physical function deficits would be reversible with this therapy.

Specific Aims and Hypotheses

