Specific Aims and Hypotheses

Aim 1. To study the effectiveness of antidepressant medications to treat depressive symptoms in older adults with PTSD/MDD.

Hyp 1: A significant improvement in depressive symptoms will be observed, and response rates to open antidepressant medication treatment in this population will be greater than 50%.

Aim 2: To evaluate change in cognition and physical function following antidepressant medication treatment.

Hyp 2: As compared to non-responders, responders to antidepressant treatment will demonstrate significantly greater improvement in executive function (NIH Toolbox) and gait speed.

Description of Subject Population

Sample #1

Specify subject population

Participants in IRB 7489 with combined PTSD and MDD

Number of completers required to accomplish study aims

20

Projected number of subjects who will be enrolled to obtain required number of completers

25

Age range of subject population

50 years and older

Gender, Racial and Ethnic Breakdown

We anticipate the sample will be composed of approximately 60% women and 40% men.

Racial/ethnic group: On the basis of previous depression studies conducted in the Clinic for Aging, Anxiety, and Mood Disorders, it is anticipated that the sample will be composed of approximately 75% Caucasian, 15% African American, and 10% Hispanic subjects.

Description of subject population

The proposed study will enroll 25 outpatients who are (1) participants in IRB 7489, (2) diagnosed with DSM 5 MDD, (3) have HRSD ≥ 18 , and (4) are willing to and capable of providing informed consent and complying with study procedures. Participants will be excluded for (1) history of allergic or adverse reaction to escitalopram and duloxetine, (2) non-response to adequate trial of escitalopram (at least 4 weeks at dose of 20mg) and duloxetine (at least 4 weeks at dose of 60mg) during the current episode, or (3) current treatment with psychotherapy, antidepressants, or other psychotropic medications.

Recruitment Procedures

Describe settings where recruitment will occur

Subjects will be recruited from participation in IRB 7489.

How and by whom will subjects be approached and/or recruited?

The research assistant will notify a study clinician once a participant completing IRB 7489 is known to meet the selection criteria. The clinician will then approach the participant and discuss potential treatment in this protocol, with its attendant risks, benefits, and alternatives.

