Hamilton Anxiety Rating Scale (HARS) 14-item scale: standard measure of anxiety severity in pharmacotherapy studies and has been shown to have good reliability and validity.

--15 minutes

24-item Hamilton Rating Scale for Depression (HRSD): standard measure of depression severity used across diverse patient samples, including PTSD.

--15 minutes

CGI Severity and Improvement: scales measuring the clinician's view of subjects' global functioning.

--1 minute

Digit Symbol test from the WAIS-III: measure of processing speed.

--2 minutes

Pattern and Letter Comparison tests: reliable measures of processing speed.

--4 minutes

Trail Making Test Part A: reliable test of motor speed.

--3 minutes

Selective Reminding Test: test of episodic memory functioning will allow us to identify deficits in episodic memory functioning consistent with a classification of amnesic mild cognitive impairment (aMCI).

--10-15 minutes

NIH-EXAMINER battery: designed to assess executive functions reliably, comprehensively, and efficiently. This battery examines working memory, inhibition, set shifting, fluency, insight, planning, social cognition and behavior.

--1 hour

NIH Toolbox Cognition Battery: brief, diverse, accessible, and psychometrically sound set of 7 computerized instruments that measure 6 ability subdomains important for cognitive health.

--45 minutes

Frailty characteristics: unintentional weight loss (10 lbs or 5% of body weight in the past year), self-reported exhaustion, weakness (grip strength), slow walking speed, and low physical activity.

--10 minutes

Pittsburgh Fatigability Scale (PFS): the only self-report measure of fatigability associated with performance and perceived exertion.

--5 minutes

Minnesota Leisure Time Physical Activity Questionnaire: measure of physical activities, with activity levels < 383 kcal considered frail.

--5 minutes

Posttraumatic Stress Disorder Checklist (PCL-5): 20-item self-report PTSD symptom screening instrument that has been shown to have good internal consistency, strong correlations with other PTSD scales, and high diagnostic efficiency.

--5-10 minutes

Clinician-Administered PTSD Scale for DSM-5 (CAPS-5): The CAPS is a 30-item instrument containing 0- 4 Likert-style item frequency and intensity scales for PTSD symptoms, with subscales for intrusion, avoidance, and hyperarousal symptom clusters, and associated affective features.

--45 minutes

Please attach copies, unless standard instruments are used

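### The SAP tests whole-sample change, so the protocol's Hypothesis 2 (responders improve more than non-responders in executive function and gait speed) is left without an analysis

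*SAP*

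**What the plan says.** Protocol, Specific Aims and Hypotheses:
- Aim 2 is broad: "To evaluate change in cognition and physical function following antidepressant medication treatment".
- Hypothesis 2, placed under that aim, is narrower and compares two groups: "As compared to non-responders, responders to antidepressant treatment will demonstrate significantly greater improvement in executive function (NIH Toolbox) and gait speed".
- Hypothesis 1 also relies on response, predicting that "response rates to open antidepressant medication treatment in this population will be greater than 50" per cent.

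SAP, Statistical Analysis (a single paragraph):
- The second hypothesis under investigation reads "2) cognitive and physical functioning will likewise significantly improve following antidepressant treatment".
- The only test named is a paired-samples t-test of change from before to after treatment. Besides the HRSD, the outcomes are "cognitive functioning (NIH Toolbox total score), and physical functioning (gait speed").
- There is no grouping factor.

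Protocol, Assessment Instruments, describes the NIH Toolbox Cognition Battery as a "set of 7 computerized instruments that measure 6 ability subdomains important for cognitive health".

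Neither document says what counts as response, and no other section of the protocol supplies a comparison of responders with non-responders.

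**The concern.** The two documents attach different hypotheses to the same aim. If the SAP is followed exactly, the trial will report no comparison of responders with non-responders and no result for an executive-function score.

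Both omissions touch the trial's stated purpose. The Lay Summary asks "are cognitive and physical function deficits in PTSD/MDD patients reversible with effective antidepressant treatment", which makes the effectiveness of treatment part of the question. The Background explains the cognitive interest: "The most prominent cognitive differences observed to date in our study between PTSD and TEHC subjects is executive dysfunction".

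The practical risk is in reporting. A significant paired t-test could be presented as support for Hypothesis 2 although it does not bear on it. If the comparison is added after the data are seen, the response cut-off, the executive-function score and the model would all be free choices. With 20 completers the result could depend on them.

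**Working it through.** **1. The hypothesis and the planned test, side by side**

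| Element | Protocol Hypothesis 2 | SAP |
|---|---|---|
| Contrast | Responders against non-responders | Whole sample, before against after |
| Cognitive outcome | Executive function (NIH Toolbox) | NIH Toolbox total score |
| Physical outcome | Gait speed | Gait speed |
| Definition of response | Not given | Not given |

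Hypothesis 2 names two outcomes, and the SAP analyses neither as stated. Gait speed lacks the responder contrast. Cognition lacks both the contrast and a score specific to executive function, since the total draws on 7 instruments and 6 subdomains. That the SAP's tests use the whole sample is an inference, but the SAP names no subgroup.

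**2. Whether the paired test could stand in for the contrast**

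Assumptions: 20 completers split 10/10, SD of change equal to 1, two-sided 5% tests, 100,000 simulated trials.

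| Scenario | Paired test significant | Between-group test significant |
|---|---|---|
| Both groups improve by 0.66 SD (Hypothesis 2 false) | 80% | 5% |
| Responders gain 0.66 SD, non-responders lose 0.66 SD (Hypothesis 2 true) | 2% | 80% |

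The second row is an extreme case, chosen to illustrate. The two tests answer different questions.

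**3. Precision of the missing contrast**

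The protocol gives 20 required completers and 25 enrolled. The 25 agrees with 20/(1 − 0.20), but a 20% dropout rate is my inference. No power, alpha, effect size or SD is stated, so the 20 cannot be reproduced. I assume two-sided alpha 0.05 and 80% power. The splits correspond to assumed response rates of 50%, 60%, 70% and 80%; the protocol says only that it expects more than 50%.

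For a difference in change scores (18 degrees of freedom), in units of the SD of change:

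half-width = t(0.975, 18) × √(1/n₁ + 1/n₂), with t(0.975, 18) = 2.101.

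At 10/10: 2.101 × √(0.1 + 0.1) = 2.101 × 0.447 = 0.940. At 16/4: 2.101 × √(0.0625 + 0.25) = 2.101 × 0.559 = 1.174.

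The difference detectable with 80% power, and the power at 0.8 SD, come from the noncentral t distribution.

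| Split | 95% CI half-width | Difference for 80% power | Power at 0.8 SD |
|---|---|---|---|
| 10/10 | 0.940 | 1.325 | 39% |
| 12/8 | 0.959 | 1.352 | 38% |
| 14/6 | 1.025 | 1.446 | 34% |
| 16/4 | 1.174 | 1.656 | 27% |

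For comparison, the planned paired test with 20 completers has a half-width of 2.093/√20 = 0.47 SD of change and needs a mean change of 0.66 SD for 80% power.

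**4. The same contrast by ANCOVA**

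With one baseline covariate (17 degrees of freedom, t = 2.110) and no baseline difference between the groups, the half-width runs from 0.944 (10/10) to 1.179 (16/4) residual SD. These are best cases. A baseline gap of d within-group SD adds d²/18 under the square root. At 10/10 with d = 1: 2.110 × √(0.2 + 1/18) = 1.067. At 16/4 with d = 1: 2.110 × √(0.3125 + 1/18) = 1.280.

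**The case against.** The strongest reply is that the SAP states its own hypotheses and tests them coherently, that the paired tests answer Aim 2 as worded, and that leaving out so weak a contrast is defensible in a small, open, single-arm study. Responder status is not randomised and is known only after treatment. Under Criteria for Early Discontinuation, dropped patients have no further research measures, so the comparison would cover completers only. All of this is true, and it limits what the contrast can show. It does not justify replacing a stated hypothesis without saying so. If the contrast is judged not worth doing, the protocol hypothesis should be amended openly.

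A second reply concerns the cognitive outcome. Hypothesis 2 names the NIH Toolbox but no particular score, and the protocol does not list the six subdomains. The only battery it describes as assessing executive functions is NIH-EXAMINER. This stands as a qualification. A reader might infer that executive function goes wholly unmeasured or is absent from the Toolbox total, and the documents do not show that. They show only that no score specific to it is analysed.

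A third reply is that ANCOVA should not be put ahead of change scores. This also stands. Hypothesis 2 speaks of greater improvement, which is literally a difference in change, and the two methods can disagree when non-randomised groups differ at baseline.

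**Conclusion.** The point holds and should be corrected before analysis: one of the protocol's two hypotheses has no analysis, and a different hypothesis stands in its place. This conclusion rests on the wording of the two documents and on no assumption about effect size.

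The precision figures do rest on assumptions: 20 completers, two-sided alpha 0.05, 80% power and splits from 10/10 to 16/4. On these, the contrast would carry a half-width of about 0.94 to 1.17 SD of change and would have 80% power only for true differences of roughly 1.3 to 1.7 SD. It would be an estimate with a wide interval, and a non-significant result would not be evidence of no difference.

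Two stronger readings should be resisted. A reader might infer that the paired t-tests are wrong or that Aim 2 is not addressed; the tests are sound for Aim 2 as worded. A reader might also infer, from Week 0 being paid at the same $25 as the brief biweekly visits against $100 for Week 8, that cognitive and physical testing is not done at Week 0. The payment schedule does not establish when tests are done, and the Lay Summary places baseline testing at Week 0 and its repeat at Week 8.

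**What to change.** Keep the paired t-tests as the Aim 2 analysis. Then take one of two routes before Week 8 data are examined.

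**Route A: add the Hypothesis 2 analysis to the SAP.**
- Compare responders with non-responders on change from pre-treatment to Week 8 in gait speed and in one executive-function score.
- Name that score in advance, from the NIH Toolbox as Hypothesis 2 specifies. The documents do not identify it, so the sponsor must.
- State the HRSD-based definition of response.
- Fix one method in advance. A difference in change scores matches the wording of Hypothesis 2; baseline-adjusted ANCOVA is an alternative.
- Report the difference with its 95% confidence interval as an associational estimate in completers, and give the number of enrolled patients without Week 8 scores.

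**Route B: amend Hypothesis 2 openly.** Restate it in the protocol as the whole-sample hypothesis, label this as a change, and draw no conclusion about responders or about executive function specifically.

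**Cost.** Route A changes SAP wording and adds one analysis; Route B changes wording in the protocol. Neither needs a new visit or measure: under Study Procedures the HRSD is rated at the biweekly contacts and at Week 8, and repeat neuropsychological testing (including the Toolbox) and gait speed are done at Week 8. The price of Route A is low precision and a non-randomised comparison. The price of Route B is giving up the responder and executive-function questions.

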3. HRSD >=18

3. Data from IRB 7489

4. Willing to and capable of providing informed consent and complying with study procedures.

4. Clinical interview

Create or insert table to describe the exclusion criteria and methods to ascertain them

Exclusion criteria:

Method of ascertainment:

1. History of allergic or adverse reaction to escitalopram and duloxetine

1. Clinical interview, data from IRB 7489

2. Non-response to adequate trial of escitalopram (at least 4 weeks at dose of 20mg) and duloxetine (at least 4 weeks at dose of 60mg) during the current episode

2. Clinical interview, data from IRB 7489

3. Current treatment with psychotherapy, antidepressants, or other psychotropic medications.

3. Clinical interview, data from IRB 7489

Waiver of Consent/Authorization

Indicate if you are requesting any of the following consent waivers

Waiver of consent for use of records that include protected health information (a HIPAA waiver of Authorization)

No

Waiver or alteration of consent

No

Waiver of documentation of consent

Yes

Waiver of parental consent

No

Consent Procedures

Is eligibility screening for this study conducted under a different IRB protocol?

Yes

Indicate NYSPI IRB #

7489

Describe Study Consent Procedures

Participants who complete IRB 7489, meet the study selection criteria and agreed to be contacted in the future will be approached by a study clinician, Psychiatrist (MD), or a Psychiatric Nurse Practitioner (NP) authorized to obtain patient consent. Study clinicians who obtain consent for this study are licensed Doctors of Medicine (MD) and/or Psychiatric Nurse practitioners (NP) in the State of New York. Participants may be approached on the day of their final study visit for protocol IRB 7489 or may be contacted by phone.

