1. Following consent, the participant will be begun on either escitalopram 10mg or duloxetine 30mg. The default medication will be escitalopram. Subjects will begin escitalopram 10mg, continue this dosage for 4 weeks, then if the HRSD >7 at Week 4, he/she will have their dosage increased to 20mg for the remainder of the 8 week study. Participants who have not responded to or not tolerated escitalopram in the current depressive episode will be started on duloxetine. They will take 30mg of duloxetine for the first 2 weeks, then, **contingent on clinical assessment that the 30mg dose is sufficiently well tolerated**, be increased to 60mg for the **remaining 6 weeks** of the study. Participants will be provided with the study medication during the Week 0 (baseline) in person visit. During the week 4 (virtual) visit, participants **taking escitalopram** will be sent the study medication directly to their home via Fedex. **This will be done during the week 2 (virtual) visit for participants taking duloxetine.** If significant worsening occurs and/or the participant wishes to be seen in person for the week 4 **or week 2** visit, they will be provided with the study medication onsite.

Study Visits will occur in person/virtually as outlined below:

- Week 0: In-person
- Week 2: Virtual
- Week 4: Virtual
- Week 6: Virtual
- Week 8: In-person

2. Subjects unable to tolerate the higher dose of study medication will have their dose reduced to the previously tolerated dose. Subjects unable to tolerate the beginning dose of study medication will be tried (if possible given their history) on the other study medication. Participants unable to tolerate the beginning dose of either study medication will be dropped from the study and enter post protocol open treatment.

3. Subjects will have telephone/video-conference visits via a telephone and/or a HIPAA compliant video conferencing platform, Webex with the research assistant and study clinician every two weeks. The RA will check Hamilton Rating Scale for Depression (HRSD) and Hamilton Anxiety Rating Scale (HARS) at each call. The study clinician will then evaluate the participant and complete the Clinical Global Impressions (CGI) Severity and Improvement. If the participant requests or significant clinical worsening in the

judgement of the study clinician occurs, then the participant will be brought to NYSPI for in person evaluation.

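### The SAP has no analysis of the predicted response rate above 50%, and neither document defines response or its denominator

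*SAP*

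**What the plan says.** Hyp 1 (protocol, Specific Aims and Hypotheses) has two parts: a significant improvement in depressive symptoms, and that "response rates to open antidepressant medication treatment in this population will be greater than 50" per cent. Hyp 2 in the same section also needs responder status: "As compared to non-responders, responders to antidepressant treatment will demonstrate significantly greater improvement in executive function", with gait speed as the second outcome.

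The SAP restates the first hypothesis without the rate: "individuals with comorbid PTSD and MDD will experience significant depressive symptom improvement with antidepressant treatment". For the HRSD it plans one analysis: "paired samples t-tests will be used to analyze the within-subject change from pre- to post-treatment on depressive symptom severity". It mentions no proportion, interval, comparison with 50%, analysis set or missing-data rule.

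The protocol plans 20 completers; the line "Projected number of subjects who will be enrolled to obtain required number of completers" gives 25. HRSD is rated at the two-weekly calls and at the Week 8 endpoint (Study Procedures, items 3 and 4). Patients who stop medication, or who meet the worsening rule, are dropped and no further research measures are taken (Criteria for Early Discontinuation). Study Procedures, item 2, adds another route out: "Participants unable to tolerate the beginning dose of either study medication will be dropped from the study and enter post protocol open treatment".

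**The concern.** The protocol commits to one number, and the SAP has nothing that estimates it. If a response rate is reported anyway, its definition and denominator will be chosen after the data are seen. Hyp 2 rests on the same undefined classification. The only post-baseline HRSD cut-off in the documents, above 7 at Week 4, is a dosing trigger and does not define response.

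The denominator is not a formality. Ineffectiveness and clinical worsening are among the listed reasons for leaving, so a rate among completers may be too favourable.

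**Working it through.** **Inputs.** From the protocol: 20 completers, 25 enrolled, reference rate 50%. Assumptions: all 25 start drug, and the 5 who are lost count as non-responders. The documents state no dropout rate; the 5 is 25 − 20, or 5/25 = 20%. This agrees with 20/(1 − 0.20) = 25, but the 20% is back-calculated, so that is a consistency check only.

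**1. Can the paired t-test stand in for the response rate?** No. With n = 20 and an assumed two-sided alpha of 0.05, the test is significant once the mean change reaches t(0.975, 19)/√20 = 0.47 SD. For an assumed SD of change of 6 to 8 points, that is a mean drop of 2.8 to 3.7 points. Suppose response means a 50% drop, changes are normal, and baseline is fixed at a value from 18 to 26 (all assumptions). The response rate is then P(change ≥ baseline/2):
- baseline 26, SD 6: P(Z ≥ (13 − 2.81)/6) = 4.5%
- baseline 18, SD 8: P(Z ≥ (9 − 3.74)/8) = 25.6%

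So a significant test is compatible with a response rate of roughly 5% to 26%.

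**2. Effect of the denominator** (exact Clopper-Pearson 95% CI)

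| Responders | Of 20 completers | Of 25 treated |
|---|---|---|
| 11 | 55% (31.5 to 76.9) | 44% (24.4 to 65.1) |
| 12 | 60% (36.1 to 80.9) | 48% (27.8 to 68.7) |

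At these two counts the point estimate changes sides of 50%. All four intervals include 50%.

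**3. How likely are 11 or 12 responders?** P(11 or 12 of 20) = P(at least 11) − P(at least 13), at assumed completer response rates:
- 60%: 0.755 − 0.416 = 0.34
- 70%: 0.952 − 0.772 = 0.18
- 75%: 0.986 − 0.898 = 0.09

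**4. What the interval can show.** A lower 95% limit above 50% needs 15/20 (50.9 to 91.3) or 18/25 (50.6 to 87.9); 17/25 gives 46.5 to 85.1. With 5 lost, 18/25 means 18 of the 20 completers, or 90%. The highest possible all-treated rate is 20/25 = 80%.

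**5. Mean HRSD change.** Let mC and mD be the mean changes in completers and leavers. The completer mean minus the all-treated mean is mC − (20mC + 5mD)/25 = (mC − mD)/5. That is 1 point for each 5-point gap, zero with no gap, and the opposite sign if leavers did better. The documents do not give the gap.

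**The case against.** Several stronger readings are tempting, and the documents do not support them.

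- *The pre- and post-treatment visits are unknown.* The SAP names neither, but the protocol calls Week 8 the study endpoint and lists the HRSD there. The Lay Summary says "Participants will be seen in person for the week 0 (baseline) visit, where they will complete baseline testing" and describes Week 8 as a repeat of that testing, so Week 0 is the ordinary baseline. The entry "3. Data from IRB 7489" is how the HRSD eligibility threshold is ascertained and does not name an analysis baseline. Confirming both visits takes one line.
- *The t-test result is at risk from dropout.* The direction of bias is plausible but not certain: preference and other reasons are listed too, non-responders can complete, and intolerance first leads to a dose reduction or a switch. With completers improving by an assumed 10 points, leavers changing by +4, 0 or −4 (positive is improvement) and within-group SDs of 6 to 12, the all-25 means are 8.8, 8.0 and 7.2, and the largest two-sided p is 0.011. The test would probably stand.
- *The denominator alters the inference at 11 or 12 responders.* It moves the point estimate only; the intervals include 50% either way.

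It can also be argued that the target of 20 completers implies a completer analysis. That figure is a recruitment target. It sets no denominator for response, and even on that reading response stays undefined. The objections narrow the point but do not answer the missing response analysis.

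**Conclusion.** The point holds and should be fixed. The omission of any response analysis and of a response definition is certain from the text. Followed exactly, the SAP leaves the protocol's only numeric hypothesis unanswered.

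The size of the denominator effect rests on 5 of 25 being lost and counted as non-responders. On that basis, 11 or 12 responders fall on different sides of 50% according to the denominator, with probability 34%, 18% or 9% at completer rates of 60%, 70% or 75%. A reader might infer that the mean HRSD result is biased by a known amount or that its significance is in doubt. Neither follows: the gap between leavers and completers is not given, and the direction is only plausible.

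**What to change.** Add to the SAP:

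1. A prespecified response definition, for example at least a 50% HRSD reduction from Week 0 to Week 8. Use all who started drug as the denominator and count early stoppers as non-responders. Show an exact 95% CI against 50% as estimation, with the completer rate alongside.
2. Confirmation that Week 0 is baseline and Week 8 is post-treatment for the HRSD.
3. Beside the completer paired t-test, one analysis of mean HRSD change that includes early stoppers. A repeated-measures model on the two-weekly ratings already collected would do, as would setting leavers' change to 0. The model is an option, not a requirement.
4. The number of dropouts and their reasons.

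The cost is a few sentences, a little more analysis work and no new visits. If no HRSD is yet planned at Week 0, it adds one rating, listed at 15 minutes under Assessment Instruments, at an existing visit. The all-treated response estimate will be lower than the completer rate whenever patients are lost (at most 80% with 5 of 25 lost), and the comparison with 50% will often be inconclusive.
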